### **6.3 Post-Study Follow-Up Period**

#### **6.3.1 Safety Follow-Up Visit**

The mandatory Safety Follow-Up Visit should be conducted 30 days +/- 7 days after the last dose of core study (i.e. after 8 cycles) treatment or EOT visit, whichever comes first. All AEs that occur prior to the Safety Follow-Up Visit should be recorded. Subjects with a treatment related AE of Grade  $\geq 1$  will be followed until the resolution of the AE to Grade 0 or until the beginning of a new anti-neoplastic therapy, whichever occurs first.

#### **6.3.1.1 *Survival Follow-Up***

Subjects will be followed every 12 weeks +/- 14 days post study for survival status and record of anti-cancer treatments for up to 5 years in follow-up until death, withdrawal of consent, or the end of the study, whichever occurs first. If the subject has any anti-cancer treatments subsequent to study completion at any time during that five year follow-up period, their subsequent treatment would be recorded. This will be done by review of patients' medical records, communication with patients treating physicians, review of public obituary records or contact of patients by telephone.

**Table 3 - STUDY SCHEMA**

Trial Period:	Screening Phase	Treatment Cycles a								End of Treatment	Post Study Treatment		
		1	2	3	4	5	6	7	8		Safety Follow-up	SOC Treatment Period (if applicable)	Survival Follow Up b
Treatment Cycle/Title:	Main Study Screening Visit									Cycle 8 or off study due to progression/toxicity			
Scheduling Window (Days):	-28 to -1		± 7	± 7	± 7	± 7	± 7	± 7	± 7	At time of Discontinuation	30 days (± 7) post discontinuation	Per SOC guidelines	Every 12 weeks (± 14 days) post discontinuation
Administrative Procedures													
Informed Consent/ Inclusion/Exclusion Criteria	X												
Prior and Concomitant Medication Review	X	X	X	X	X	X	X	X	X	X	X		
Pembrolizumab		X	X	X	X	X	X	X	X			X	
SFRT		X											
Survival Status/ Post-study anticancer therapy status											X	X	X
Clinical Procedures/Assessment													
Review Adverse Events	X	X	X	X	X	X	X	X	X	X	X		
Full Physical Examination	X e												
Directed Physical Examination	X	X	X	X	X	X	X	X	X	X	X		
ECOG Performance Status	X	X	X	X	X	X	X	X	X				
Local Laboratory Procedures/Assessments													
Pregnancy Test – Urine or Serum β-HCG	X i												
CBC with Differential	X f		X	X	X	X	X	X	X				
Comprehensive Metabolic Panel	X f		X	X	X	X	X	X	X				
T3, FT4 and TSH	X f			X		X		X					
Efficacy Measurements													
Tumor Imaging c	X g			X		X		X				X h	
Tumor Biopsies/Archival Tissue Collection/Correlative Studies Blood													
Archival or Newly Obtained Tissue Collection	X d			X d									

CASE 1516

Protocol Amendment 7

06/06/2019

Peripheral Blood/Flow	X			X		X			X			
Serum	X			X		X			X			
PBMC/IRC	X		X	X	X	X	X	X	X			

## 6.4 Study Schema

- a) Patients will begin pembrolizumab on the same day as the SFRT but no greater than 3 days after the SFRT. Patients will receive subsequent Pembrolizumab every 3 weeks ( $\pm$  7 days per protocol) until progression or unacceptable toxicity. A treatment break for up to 6 weeks will be allowed upon discussion with study PI. The core study period will end at 8 cycles. After cycle 8 (End of Treatment visit) patients will continue pembrolizumab as standard of care if they are tolerating and have no disease progression.
- b) Patients will be monitored post study every 12 weeks ( $\pm$  14 days) for survival status; these could be done by review of patient's medical records or contacting patient's medical provider or the subject. Patients on standard of care pembrolizumab will begin survival follow up after pembrolizumab progression or start of new anti-neoplastic therapy.
- c) Patient's disease will be monitored with CT scans of the chest and abdomen after every 2 cycles (i.e. prior to every odd cycle  $\pm$  7 days) or sooner, if clinically indicated, while on study treatment. CT scans of the pelvis will be completed only for known pelvic disease or pelvic symptoms as clinically indicated.
- d) Patients must be willing to provide archival tissue of any age or obtain a fresh biopsy at screening. If available, tissue collected  $<6$  weeks from the start of study treatment is recommended. If a previous PDL1 status is obtained, a patient may be eligible for a tissue exemption from the sponsor investigator. Patients must be willing to provide a repeat treatment biopsy after 2 cycles of pembrolizumab, before cycle 3 imaging is performed. Both baseline and treatment biopsies can be evaluated on a case by case basis and an exception may be made at the discretion of the sponsor investigator.
- e) Consult radiation oncologist for radiation simulation consult. This can be done on the same day or a different day of patient's oncology physical exam as long as it is within the 28 day screening window.
- f) Screening laboratory tests are to be performed within 10 days prior to the first dose of study drug.
- g) Imaging can be done within 30 days of start of treatment
- h) Patients on standard of care pembrolizumab beyond the 8 cycles of study treatment, will have CT scans every 9 weeks ( $\pm$  14 days).
- i) For female subjects of reproductive potential, a urine or serum pregnancy test must be performed within 72 hours prior to first dose of trial treatment.

CASE 1516

Protocol Amendment 7

06/06/2019

## **6.5 Definition of Dose Limiting Toxicity**

For the purpose of determining the safety of SFRT and pembrolizumab combination, a DLT will be considered to be any of the following adverse events which are probably or definitely attributable to study treatment, and which occur between the SFRT and within 60 days of the last fraction of SFRT.

1. Any non-hematologic, non-laboratory toxicity which is grade 3 or greater and does not resolve to grade 2 or lower with supportive care within 14 days.
2. Any non-hematologic, non-laboratory toxicity which is grade 4 or greater

For patients with lung targets, the development of grade 3 or greater pneumonitis that is probably or definitely attributable to either SFRT or pembrolizumab within the follow-up period will be considered a DLT, regardless of whether it resolves

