#### **2.2.3 Safety Endpoints**

1. Adverse Events as characterized by type, frequency, severity (as graded by National Cancer Institute Common Terminology Criteria for Adverse Events [NCI CTCAE] v4.0), timing, seriousness and relationship to study treatments
2. For patients receiving SFRT to lung lesions, the development of grade 3 or greater pneumonitis that is probably or definitely attributable to either SFRT or pembrolizumab within the follow-up period will be monitored

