##### **4.1.5.3 *Subsequent Anti-Cancer Therapy Status***

The investigator or qualified designee will review all new anti-neoplastic therapy initiated after the last dose of trial treatments. The safety follow-up visit should occur 30-days (+/- 7 days) after discontinuation of Pembrolizumab or prior to the start of a new anti-cancer therapy, whichever occurs first. Once new anti-cancer therapy has been initiated, the subject will move into survival follow-up.

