### **6.9 Withdrawal/Discontinuation**

Subjects may withdraw consent at any time for any reason or be dropped from the trial at the discretion of the investigator should any untoward effect occur. In addition, a subject may be withdrawn by the investigator or the Sponsor if enrollment into the trial is inappropriate, the trial plan is violated, or for administrative and/or other safety reasons. When a subject discontinues/withdraws prior to trial completion, all applicable activities scheduled for the final trial visit should be performed at the time of discontinuation. Any adverse events which are present at the time of discontinuation/withdrawal should be followed in accordance with the safety requirements outlined in Section 7.2 - Assessing and Recording Adverse Events. Subjects who a) attain a CR or b) complete 24 weeks of treatment with pembrolizumab may discontinue treatment with the option of restarting treatment if they meet the criteria specified in Section 6.9.1. After discontinuing treatment following assessment of CR, these subjects should return to the site for a Safety Follow-up Visit (described in Section 6.3.1) and then proceed to the Follow-Up Period of the study (described in Section 6.3.1.1).

A subject must be discontinued from the trial for any of the following reasons:

- The subject or legal representative (such as a parent or legal guardian) withdraws consent.
- Confirmed radiographic disease progression

*Note: A subject may be granted an exception to continue on treatment with confirmed radiographic progression if clinically stable or clinically improved.*

CASE 1516

Protocol Amendment 7

06/06/2019

- Unacceptable adverse experiences as described in Section Intercurrent illness that prevents further administration of treatment
- Investigator's decision to withdraw the subject
- The subject has a confirmed positive serum pregnancy test
- Noncompliance with trial treatment or procedure requirements
- The subject is lost to follow-up
- Administrative reasons

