From the time of treatment through 30 days following cessation of treatment, all adverse events must be reported by the investigator. Such events will be recorded at each examination on the Adverse Event case report forms/worksheets. The reporting timeframe for adverse events meeting any serious criteria is described in section 7.5.1. The investigator will make every attempt to follow all subjects with non-serious adverse events for outcome.

Adverse events will not be collected for subjects during the pre-screening period (for determination of archival tissue status) as long as that subject has not undergone any protocol-specified procedure or intervention. If the subject requires a blood draw, fresh tumor biopsy etc., the subject is first required to provide consent to the main study and AEs will be captured according to guidelines for standard AE reporting.

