#### **7.5 Immediate Reporting of Adverse Events to the Sponsor and to Merck**

##### **7.5.1 Serious Adverse Events**

A serious adverse event is any adverse event occurring at any dose or during any use of Merck's product that:

- Results in death
- Is life threatening
- Results in persistent or significant disability/incapacity
- Results in or prolongs an existing inpatient hospitalization

- Is a congenital anomaly/birth defect
- Is another important medical event

*Note: In addition to the above criteria, adverse events meeting either of the below criteria, although not serious per ICH definition, are reportable to the Merck in the same timeframe as SAEs to meet certain local requirements. Therefore, these events are considered serious by Merck for collection purposes.*

- Is a new cancer (that is not a condition of the study)
- Is associated with an overdose.

Refer to Table 7 for additional details regarding each of the above criteria.

For the time period beginning when the consent form is signed until treatment, any serious adverse event, or follow up to a serious adverse event, including death due to any cause other than progression of the cancer under study (reference Section 7.2 for additional details) that occurs to any subject must be reported within 1 business day to the Sponsor and within 2 working days to Merck Global Safety if it causes the subject to be excluded from the trial, or is the result of a protocol-specified intervention, including but not limited to washout or discontinuation of usual therapy, diet, placebo treatment or a procedure.

For the time period beginning at treatment through 90 days following cessation of treatment, or 30 days following cessation of treatment if the subject initiates new anticancer therapy, whichever is earlier, any serious adverse event, or follow up to a serious adverse event, including death due to any cause other than progression of the cancer under study whether or not related to the Merck product, must be reported within 1 business day to the Sponsor and within 2 working days to Merck Global Safety.

Additionally, any serious adverse event, considered by an investigator who is a qualified physician to be related to Merck product that is brought to the attention of the investigator at any time following consent through the end of the specified safety follow-up period (Section 6.3) must be reported immediately to the Sponsor and to Merck Global Safety.

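### DLTs are counted to day 60 after radiation, but in patients who stop early the collection of all adverse events ends before day 60, so some DLTs could go unrecorded

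*Combined protocol and SAP*

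**What the plan says.** All references are to the combined protocol and SAP.

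- **DLT window.** Section 6.5 counts events probably or definitely attributable to study treatment "which occur between the SFRT and within 60 days of the last fraction of SFRT". They are non-haematologic, non-laboratory events that are either grade 3 or worse and not down to grade 2 within 14 days, or grade 4 or worse.
- **All adverse events.** Section 7.2: "From the time of treatment through 30 days following cessation of treatment, all adverse events must be reported by the investigator". Section 6.9 also gives 30 days. Section 6.3.1 records events up to a safety visit timed from the last core dose or the end-of-treatment visit, whichever is first. Table 3 and 4.1.5.3 time that visit from discontinuation.
- **New therapy.** Section 4.1.5.3 brings the safety visit forward if new anticancer therapy starts, and then: "Once new anti-cancer therapy has been initiated, the subject will move into survival follow-up".
- **Serious events.** Section 7.5.1 has a longer window, "through 90 days following cessation of treatment, or 30 days following cessation of treatment if the subject initiates new anticancer therapy", whichever is earlier, related or not.
- **Pneumonitis.** For patients with lung targets, section 6.5 says that grade 3 or greater attributable pneumonitis "within the follow-up period will be considered a DLT, regardless of whether it resolves". Section 2.2.3 lists the matching safety endpoint, attributable to "either SFRT or pembrolizumab within the follow-up period will be monitored".
- **Schedule.** Table 3 has no adverse event review in the standard-of-care treatment or survival follow-up columns.

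**The concern.** A 60-day DLT definition can be applied in full only to patients who are watched for 60 days. Here the observation period is tied to the end of treatment and the DLT window to radiation. The two cover the same ground only if treatment lasts long enough. Patients who stop after one or two doses are the ones who may leave collection too soon, and early stopping is not a random event.

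The safety of radiation combined with pembrolizumab is a secondary objective, and 6.5 states that the DLT definition serves it. If late events in early stoppers are not collected, and nothing says who is evaluable for DLTs, a reported DLT count can only err downward. Section 6.5.1.2 itself accepts that pembrolizumab events may appear months after the last dose, so late onset is expected. The pneumonitis endpoint has a related weakness: its window is named but not defined, and no adverse event review is scheduled after the safety visit.

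**Working it through.** The documents give no DLT rate and no DLT calculation, so there is no figure to reproduce.

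**Inputs** (radiation is day 0)
- DLT window: day 0 to day 60 (6.5).
- First dose: day 0 to 3 (Table 2). Cycles: 21 days, ±7 after cycle 1 (6.2.1).
- All-event collection: 30 days (6.3.1, 6.9, 7.2). Serious events: 90 days, or 30 with new therapy (7.5.1).
- Median PFS on pembrolizumab alone: 3.0 months in previously treated patients, 3.7 in all patients (1.1.4).

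**Step 1. Calendar, counting from the last dose.** Collection ends at last-dose day + 30, and gap = max(0, 60 − end day).

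| Doses | Last dose (day) | All-event end | Gap (days) | Gap with ±7 | Serious-event end, no new therapy |
|---|---|---|---|---|---|
| 1 | 0–3 | 30–33 | 27–30 | 27–30 | 90–93 |
| 2 | 21–24 | 51–54 | 6–9 | 0–16 | 111–114 |
| 3 | 42–45 | 72–75 | 0 | 0 | 132–135 |

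The one-dose gap is 27/60 to 30/60 of the window (45–50%). The nominal two-dose gap is 6/60 to 9/60 (10–15%).

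**Step 2. Counting from discontinuation instead (Table 3, 4.1.5.3).** A patient taken off at the first scan, about day 42, is followed to 42 + 30 = day 72, so the two-dose gap closes unless new therapy starts sooner. After one dose the gap is 30 − d days, where d is the day of discontinuation. If the decision is made when cycle 2 falls due (day 21–24), 6–9 days remain uncovered.

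**Step 3. What serious-event reporting recovers.** Without new therapy, serious events are reported past day 60 even after one dose. Life-threatening, fatal and hospitalised events are therefore caught. Two groups are left:
- new-onset, non-serious grade 3 events after the all-event cut-off that last beyond 14 days;
- any DLT past the cut-off once new therapy has started, because serious-event reporting then also ends at 30 days.

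**Step 4. Illustrative size.** Assume exponential progression times, dosing stopped by progression alone, an even DLT hazard over 60 days and the last-dose reading. F(t) = 1 − 0.5^(t/m), with 30.4375 days per month.
- m = 3.0 months (91.3 days): F(21) = 14.74%, F(42) = 27.30%.
- m = 3.7 months (112.6 days): F(21) = 12.12%, F(42) = 22.78%.

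Unobserved share = F(21) × gap₁/60 + [F(42) − F(21)] × gap₂/60.
- m = 3.0: 0.1474 × 0.50 + 0.1256 × 0.15 = 9.3%; with the shorter gaps, 0.1474 × 0.45 + 0.1256 × 0.10 = 7.9%.
- m = 3.7: 0.1212 × 0.50 + 0.1065 × 0.15 = 7.7%; with the shorter gaps, 0.1212 × 0.45 + 0.1065 × 0.10 = 6.5%.

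If all this progression were found only at the first scheduled scan, everyone affected would have had two doses. The share would then be 0.2278 × 6/60 = 2.3% to 0.2730 × 9/60 = 4.1%.

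The 6.5–9.3% is an upper figure in that serious-event capture and treatment beyond progression reduce it. It leaves out withdrawals for toxicity and safety visits brought forward for new therapy, which would add to it.

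**The case against.** The plan has more safety follow-up than the 30-day rule alone suggests. A reader might infer that adverse events are collected only to 30 days. That is true of all-event collection but not of serious events, which run to 90 days without new therapy. Treatment-related events already present are followed to grade 0 or new therapy (6.3.1), and every grade change is recorded (7.1). An event that starts inside the 30 days and then worsens or persists is therefore seen, unless new therapy intervenes. The two-dose gap also depends on reading the clock from the last dose. All of this stands, and it narrows the point to the two groups in Step 3.

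Other stronger readings also fail:
- **That the 10-patient safety rule is biased low.** Section 6.5.2 words its DLT around grade 3 or greater events during radiation treatment, so an effect of the later part of the 60 days is not shown.
- **That a planned DLT rate is understated by a known amount.** Section 8 plans toxicity counts and percentages, with no DLT-rate estimate, and no section says that unobserved patients count as DLT-free.
- **That the 23–27% progressed by week 6 are missed DLTs.** They are patients who might stop early. Section 6.9 asks for confirmed progression and allows exceptions.
- **That pneumonitis surveillance is promised for five years.** Section 6.9 says that patients who stop after a complete response "then proceed to the Follow-Up Period of the study (described in Section 6.3.1.1", which is survival follow-up. That sentence does not define the term used in 2.2.3 and 6.5.

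Ending collection at new therapy is a consistent choice in 4.1.5.3, 6.3.1 and 7.5.1, and it has a reason: attribution becomes harder. That is a real cost of the fix, but it does not make the two windows agree.

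**Conclusion.** The point holds in a limited form. The DLT window and the collection windows do not match. Patients who stop after one dose, and on the last-dose reading usually those who stop after two, leave all-event collection before day 60. From three doses on there is no gap unless new therapy cuts collection short.

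Any bias in the DLT count is downward and probably modest. The 6.5–9.3% of window time rests on an exponential PFS borrowed from pembrolizumab alone, an even hazard and the last-dose reading, before serious-event capture. The documents do not allow the number of missed DLTs to be derived. The windows should still be aligned, because the gap falls on a stated safety objective and costs little to close. The pneumonitis endpoint needs a defined window for the same reason.

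**What to change.** 1. Reconcile 6.5, 6.3.1, 7.2, 7.5.1 and Table 3 so that potential DLTs are collected through the later of the 30-day safety visit and day 60 after radiation, including after new therapy starts. A remote contact or record review would do for early discontinuers. Record the start date of any new therapy so that attribution can be judged.
2. State one starting point, last dose or discontinuation, for the safety visit in 4.1.5.3, 6.3.1 and Table 3.
3. In 2.2.3 and 6.5, tie grade 3 or greater pneumonitis to a window in which adverse events are actually collected.
4. In section 8, report DLTs among patients observed to day 60 or with a DLT, and give the number not observed to day 60.

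**Cost:** amendment wording and one extra contact for early discontinuers. Under the illustration that is about 0.2278 × 48 = 11 to 0.2730 × 48 = 13 patients. Attribution will be harder after new therapy starts, and the reported DLT count may be slightly higher.

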### **6.5.1 Pembrolizumab Dose Selection/Modification**

#### **6.5.1.1 *Dose Selection***

The rationale for selection of doses to be used in this trial is provided in Sections 1.1 and 1.3.

Details on preparation and administration of pembrolizumab (MK-3475) are provided in the Pharmacy Manual.

#### **6.5.1.2 *Dose Modification (Escalation/Titration/Other)***

Adverse events (both non-serious and serious) associated with pembrolizumab exposure may represent an immunologic etiology. These adverse events may occur shortly after the first dose or several months after the last dose of treatment. Pembrolizumab must be withheld for drug-related toxicities and severe or life-threatening AEs as per Table 4. See Section 6.6 for supportive care guidelines, including use of corticosteroids.

**Table 4** - Dose Modification Guidelines for Drug-Related Adverse Events

Toxicity	Hold Treatment For Grade	Timing for Restarting Treatment	Treatment Discontinuation
Diarrhea/Colitis	2-3	Toxicity resolves to Grade 0-1	Toxicity does not resolve within 12 weeks of last dose or inability to reduce corticosteroid to 10 mg or less of prednisone or equivalent per day within 12 weeks
	4	Permanently discontinue	Permanently discontinue
AST, ALT, or Increased Bilirubin	2	Toxicity resolves to Grade 0-1	Toxicity does not resolve within 12 weeks of last dose
	3-4	Permanently discontinue (see exception below) a	Permanently discontinue
Type 1 diabetes mellitus (if new onset) or Hyperglycemia	T1DM or 3-4	Hold pembrolizumab for new onset Type 1 diabetes mellitus or Grade 3-4 hyperglycemia associated with evidence of beta cell failure	Resume pembrolizumab when patients are clinically and metabolically stable
Hypophysitis	2-4	Toxicity resolves to Grade 0-1. Therapy with pembrolizumab can be continued while endocrine replacement therapy is instituted	Toxicity does not resolve within 12 weeks of last dose or inability to reduce corticosteroid to 10 mg or less of prednisone or equivalent per day within 12 weeks
Hyperthyroidism	3	Toxicity resolves to Grade 0-1	Toxicity does not resolve within 12 weeks of last dose or inability to reduce corticosteroid to 10 mg or less of prednisone or equivalent per day within 12 weeks
	4	Permanently discontinue	Permanently discontinue
Hypothyroidism		Therapy with pembrolizumab can be continued while thyroid replacement therapy is instituted	Therapy with pembrolizumab can be continued while thyroid replacement therapy is instituted
Infusion related reaction	2 b	Toxicity resolves to Grade 0-1	Permanently discontinue if toxicity develops despite adequate premedication
	3-4	Permanently discontinue	Permanently discontinue
Pneumonitis	2	Toxicity resolves to Grade 0-1	Toxicity does not resolve within 12 weeks of last dose or inability to reduce corticosteroid to 10 mg or less of prednisone or equivalent per day within 12 weeks
	3-4	Permanently discontinue	Permanently discontinue
Renal and urinary disorders - Other, specify	2	Toxicity resolves to Grade 0-1	Toxicity does not resolve within 12 weeks of last dose or inability to reduce corticosteroid to 10 mg or less of prednisone or equivalent per day within 12 weeks
	3-4	Permanently discontinue	Permanently discontinue
All Other Drug-Related Toxicity c	3 or Severe	Toxicity resolves to Grade 0-1	Toxicity does not resolve within 12 weeks of last dose or inability to reduce corticosteroid to 10 mg or less of prednisone or equivalent per day within 12 weeks
	4	Permanently discontinue	Permanently discontinue

